### 2.2. Study Objectives, Endpoints, and Estimands

Objectives/ Endpoints	Type of Endpoints [categorical (including binary), continuous, or time to endpoints]
Primary	
The primary objective of this study is to determine whether tofacitinib improves the clinical outcomes of patients with moderate SARS-CoV-2 infection as determined by the Primary outcome measure.	Binary endpoint

Endpoint: Proportion of subjects alive and not needing any form of mechanical ventilation, high flow oxygen, or ECMO by day 14 and day 30.	
Secondary	
Clinical improvement (defined as a 2-point increase) as measured by NIAID 8-point ordinal scale (i.e., 1 = death and 8 = Not hospitalized, no limitations on activities) at day 14.	Categorical endpoint
Clinical status using ordinal scale (days 3 through day 14): The ordinal scale is an assessment of the clinical status at the first assessment of a given study day. The scale is as follows: 1) Death; 2) Hospitalized, on invasive mechanical ventilation or extracorporeal membrane oxygenation (ECMO); 3) Hospitalized, on non-invasive ventilation or high flow oxygen devices; 4) Hospitalized, requiring supplemental oxygen; 5) Hospitalized, not requiring supplemental oxygen - requiring ongoing medical care (COVID-19 related or otherwise); 6) Hospitalized, not requiring supplemental oxygen - no longer requires ongoing medical care; 7) Not hospitalized, limitation on activities and/or requiring home oxygen; 8) Not hospitalized, no limitations on activities.	Categorical endpoint
Time to recovery (Day of recovery is defined as the first day on which the subject satisfies one of the following three categories from the clinical status of ordinal scale: 6) Hospitalized, not requiring supplemental oxygen - no longer requires ongoing medical care; 7) Not hospitalized, limitation on activities and/or requiring home oxygen; 8) Not hospitalized, no limitations on activities) through day 14 and day 30 from day 1.	Time to endpoint.
Time to clinical improvement (defined as a 2-point increase on the ordinal scale).	Time to endpoint
Clinical status on ordinal scale at day 30, 60, and 90.	Categorical endpoint
Mortality rate at day 30, 60 and 90.	Binary endpoint
Proportion of patients requiring ICU admission and mechanical ventilatory support (defined as clinical status of 2 and hospitalization status = ICU) at 14 and 30 days.	Binary endpoint

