### 2.2.1. Estimands

The estimand with treatment policy strategy will be utilized. All observed data (regardless of whether an intercurrent event occurs) will be included in the analysis. It includes the following 4 attributes:

- Population: Participants with COVID-19 pneumonia who meet all inclusion/exclusion criteria. The analysis will consider all observed data without employing any imputation for missing data;
- Variable: Yes or No for the occurrence of the event for categorical endpoints (including Binary endpoints), change from baseline for continuous endpoints and time to event for time to event endpoints.
- Intercurrent event(s): discontinuation of study intervention due to any reason or receiving rescue therapy.
- Population level summary: Proportion for categorical endpoints (including binary endpoints), mean for continuous endpoints and median time to event for time to event endpoints.

[figure not shown]

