### **5.2.3. Analyses for Time-to-Event Endpoints**

For time to recovery and time to clinical improvement

- If subject died prior to or on the specified time point (Day 14 or Day 30), the result for time to event will be censored on the date of death regardless of if subjects have experienced recovery or clinical improvement prior to Death.
- If no death is recorded through the specified time point (Day 14 or Day 30): For a participant who experiences the event of recovery/clinical improvement through Day 14 or Day 30, the time to event will be the study day corresponding to the earliest visit date at which the participant has already experienced the event.
- For all participants who have not experienced the event, their time to event will be right censored at the last available measurement time of the clinical status through Day 14 or Day 30.

Time to event endpoints will be analyzed using the Estimand with treatment policy strategy specified in Section 2.2.1.

The number of participants, number and percent of participants censored, and participants with recovery or clinical response will be provided for each treatment group. The median and quartiles time to event will be estimated by the Kaplan-Meier method.

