### **5.3. Methods to Manage Missing Data**

All data will be evaluated as observed, and no imputation method for missing values will be used.

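### SAP 5.2.3 censors at death even when recovery or improvement was already observed, so observed events are lost and the Day-14 and Day-30 tables can contradict each other

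*SAP*

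**What the plan says.** SAP 5.2.3 has three rules for time to recovery and time to clinical improvement, each applied at Day 14 and at Day 30. Under the first, a participant who dies on or before the horizon is "censored on the date of death regardless of if subjects have experienced recovery or clinical improvement prior to Death". The second records an event time only for participants with no death through the horizon. The third right-censors participants without the event at their last clinical-status measurement. The outputs are the numbers and percentages censored and with the event, and "The median and quartiles time to event will be estimated by the Kaplan-Meier method".

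Other parts of the plan bear on this:

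- SAP 2.2 (repeated in SAP 3.2): "Day of recovery is defined as the first day on which the subject satisfies one of the following three categories". No condition on later survival is attached.
- SAP 5.2.3: "Time to event endpoints will be analyzed using the Estimand with treatment policy strategy specified in Section 2.2.1".
- SAP 2.2.1: "All observed data (regardless of whether an intercurrent event occurs) will be included in the analysis". The intercurrent events listed are "discontinuation of study intervention due to any reason or receiving rescue therapy". Death is not among them.
- SAP 5.3: "All data will be evaluated as observed, and no imputation method for missing values will be used".
- Protocol 6.5.10 right-censors subjects who finish without the event or withdraw before it. Protocol 6.5 lets the SAP depart from the protocol, but SAP 2.1 declares only that hypothesis tests are dropped.
- Protocol 6.5.2 also prescribes Kaplan-Meier for these two endpoints.

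**The concern.** If recovery is the first day in an eligible category, a later death cannot undo it. The censoring rule nevertheless reclassifies that participant as not having recovered, and keeps the participant in the risk set as unrecovered until the day of death. Because the rule is applied separately at each horizon, one participant can be an event in one table and censored in the other.

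A second, lesser issue is one of method. A participant who dies without recovering is also censored at death. Kaplan-Meier then treats that participant as still able to recover, which overstates recovery when others recover later. This contradicts nothing in the documents, but the estimand section says nothing about death.

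At stake are the event counts, percentages, medians and quartiles for both endpoints. With hypothesis tests dropped, these summaries are the whole planned report on them. Mortality and ordinal status are tabulated separately, but deaths are not split into those before and after recovery, so a reader could not undo the rule.

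**Working it through.** The plan states no figure on this point, so there is none to reproduce. The check applies the rules literally and then measures the effect on assumed data.

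**1. Two test participants**

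| Course | Day-14 table | Day-30 table | First-event rule, both tables |
|---|---|---|---|
| Recovers Day 5, dies Day 12 | censored Day 12 | censored Day 12 | event Day 5 |
| Recovers Day 5, dies Day 20 | event Day 5 | censored Day 20 | event Day 5 |

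**2. Inputs and formula.** SAP 7 reports 24 randomized. Allocation is 1:1 in protocol 5.1 and 6.4.2 but 2:1 in SAP 2.3, so arms of 12, 16 and 8 are shown. Recovery and death days are assumptions. Non-recoverers are censored at Day 30 unless stated. Events precede censorings at ties. Estimated recovery is 1 − S, with S = ∏(1 − d/n) over event days.

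**3. One recovery erased.** Half the arm recovers by Day 11, and the Day-5 recoverer dies on Day 20. Recovery days are 4, 5, 6, 8, 9, 11 (arm of 12), daily from 4 to 11 (arm of 16), and 5, 6, 8, 9 (arm of 8). For the arm of 12 under the SAP rule, S = (11/12)(10/11)(9/10)(8/9)(7/8) = 7/12.

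| Arm | First-event: events/censored, 1 − S | SAP rule: events/censored, 1 − S |
|---|---|---|
| 12 | 6/6, 50% | 5/7, 41.7% |
| 16 | 8/8, 50% | 7/9, 43.8% |
| 8 | 4/4, 50% | 3/5, 37.5% |

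The fall in the event percentage is 1/n: 8.3, 6.3 and 12.5 points.

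**4. Does the rule carry out an intent that death cancels recovery?** In the arm of 12, let the Day-5 recoverer die on Day 7. Then S = (11/12)(10/11)(8/9)(7/8)(6/7) = 0.556 and 1 − S = 44.4%. That is neither 6/12 = 50% (recovery counts) nor 5/12 = 41.7% (death cancels it), because the censored participant is credited with a share of later recoveries.

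**5. Quantiles.** These arm sizes are chosen so that no step falls exactly on 0.50 or 0.75, and tie conventions do not matter. The Day-5 recoverer dies on Day 20.

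- Arm of 11, recoveries on Days 4, 5, 6, 8, 9, 11, 13: first quartile moves from Day 6 to Day 8, median from Day 11 to Day 13.
- Arm of 13, recoveries on Days 4, 5, 6, 8, 9, 11, 12, 13: first quartile moves from Day 8 to Day 9, median from Day 12 to Day 13.

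**6. The two tables from one data set.** Arm of 12: A recovers Day 5 and dies Day 10; B recovers Day 6 and dies Day 25; eight others recover on Days 4, 7, 8, 9, 11, 12, 18 and 21; two never recover. Estimated recovery by Day 14:

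- Day-14 table: S = (7/12)(5/6)(4/5) = 0.389, so 61.1%.
- Day-30 table: S = (8/12)(6/7)(5/6) = 0.476, so 52.4%.
- First-event rule: 8/12 = 66.7% in both.

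**7. Unrecovered deaths (the method point).** In the arm of 12 of step 3, with every recovery kept (50%), suppose k of the non-recoverers die on Day 5. Then S = (10/12) × (5/9), (4/8) or (2/6) for k = 1, 2 or 4, and estimated recovery is 53.7%, 58.3% or 72.2%. If those deaths fall on Day 12, after the last recovery, there is no effect. The two effects oppose each other: two unrecovered deaths on Day 5, plus the Day-4 recoverer dying on Day 20, give S = (11/12)(5/9) = 0.509. That is 49.1% with 5/7, against 50% with 6/6.

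**The case against.** The best defence is that the rule is deliberate. Its wording shows that the authors considered recovery followed by death, and not counting that as success is a defensible aim. Specific text usually governs general text, so the counts would be correct under the stated rule. That fails on execution: step 4 shows that censoring at death delivers neither meaning, and step 6 shows that it gives different answers at the two horizons.

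Several narrower points stand. SAP 5.3 concerns missing values and is weak support. SAP 2.2.1 does not list death, so it leaves the matter partly open, although its inclusion of all observed data still weighs against the rule. The strongest conflict is with the first-day definition. Departing from protocol 6.5.10 is permitted and is only undeclared. The treatment of unrecovered deaths is a choice of method. The Day-14/Day-30 disagreement needs an event by Day 14 and a death on Days 15 to 30. It also needs a Day-30 recovery table, which SAP 2.2 and 5.2.3 call for but SAP 3.2 does not, since it gives Day 14 only. The scenarios are hypothetical.

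**Conclusion.** The concern holds. As written, SAP 5.2.3 removes observed recoveries and improvements from participants who later die within the horizon, contrary to the SAP's own definition. It can also classify one participant differently in the two tables. Each such participant costs an arm one event, about 6 to 13 percentage points for arms of 8 to 16, and can shift the first quartile or median by one or two days in the examples. The direction of the net bias depends on how many deaths occur before and after recovery, and when.

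The sizes rest on assumed recovery and death days, because the documents report none. The main effect is zero unless a recovered or improved participant dies by the horizon. Two secondary endpoints are affected, descriptively only, and the primary endpoint is not. This should be fixed, but it does not threaten the trial's main result.

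**What to change.** In SAP 5.2.3:

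1. Set the event time to the first study day on which recovery (or improvement) is met through the horizon, whether or not death follows. Delete the no-death condition that opens the second rule.
2. Keep a participant who dies without the event in the risk set and censor at Day 14 or Day 30. Alternatively, report the Aalen-Johansen cumulative incidence with death as a competing event and read the quantiles from it. Choose one. They agree when there is no other censoring but can differ otherwise. With the arm of 12, two unrecovered deaths on Day 5 and two others censored on Day 7, the first gives 1 − (9/12)(4/7) = 57.1% and the second 3/12 + 3 × (7/12)/5 = 60.0%.
3. Restrict censoring at the last clinical-status measurement to participants alive without the event.

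If the authors do want death to cancel an earlier recovery, they should redefine the endpoint that way and hold those participants as unrecovered to one common horizon.

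In SAP 2.2.1, state how death is handled for these endpoints. In SAP 2.1, declare and justify any rule that still differs from protocol 6.5.10. Reconcile the recovery horizon in SAP 3.2 with SAP 2.2 and 5.2.3. Tabulate deaths before and after recovery by arm, and state the quantile convention for ties.

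The cost is a few lines of SAP text, a recoded censoring variable and one small table. No new data are needed.

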### **5.3. Methods to Manage Missing Data**

All data will be evaluated as observed, and no imputation method for missing values will be used.

## **6. ANALYSES AND SUMMARIES**

### **6.1. Primary Endpoint(s)**

The primary endpoint of proportion of subjects alive and not needing any form of mechanical ventilation, high flow oxygen, or ECMO by day 14, will be analyzed as described in Section 5.2.1 by treatment group based on FAS defined in Section 4.

### **6.2. Secondary Efficacy Endpoint(s)**

The secondary efficacy endpoints are listed in Section 3.2.

For the categorical (including binary) endpoints, results will be analyzed as described in Section 5.2.1 by treatment group based on FAS defined in Section 4.

For continuous endpoints, results will be analyzed as described in Section 5.2.2 by treatment group based on FAS defined in Section 4.

For time to endpoints, results will be analyzed as described in Section 5.2.3 by treatment group based on FAS defined in Section 4.

### 6.3. Subset Analyses

N/A

### 6.4. Baseline and Other Summaries and Analyses

#### 6.4.1. Baseline Summaries

The following demographics and Baseline characteristics will be summarized by treatment group and for total.

- Gender (female, male)
- Race (American Indian or Alaska Native, Asian, Native Hawaiian or other Pacific Islander, Black or African American, White, more than one race and not reported)
- Ethnicity (Hispanic or Latino, Not Hispanic or Latino and unknown or not reported)
- NIAID ordinal scale of disease severity scores (i.e., 1 = death and 8 = Not hospitalized, no limitations on activities)
- Prothrombin time/partial prothrombin time (PT/PTT)
- Days since onset of symptoms
- Days since diagnosis
- Fibrinogen
- D-dimer
- Hs-CRP
- Ferritin
- Procalcitonin
- LDH
- Tobacco history (type of substance, Usage (Never, current and former)
- Height
- Weight

#### 6.4.2. Study Conduct and Participant Disposition

Participants evaluation for FAS and SAS, disposition, and discontinuation will be summarized by treatment group and for total.

#### 6.4.3. Study Intervention Compliance

- Actual Dosing Days (ADY) is defined as the total number of dosing days on which study drug was administered.
- Exposure Time is defined as the total number of days from first to and including last day of study dosing (Last Oral Dosing Date - First Oral Dosing Date + 1);
- Dose Compliance is defined as the number of doses of study drug the subject took out of the expected total number of doses of study drug
  - ADY1 = Date of returning to clinical baseline – Date of first dosing (Day 1) + 1
  - Expected Doses (by mg):

(a)  $ADY1 \geq 14$ , Expected Doses =  $14 * 20 \text{ mg} = 280 \text{ mg}$ ;

(b)  $ADY1 < 14$ , Expected Doses =  $ADY1 * 20 \text{ mg} + (14 - ADY1) * 10 \text{ mg} = (140 + 10 * ADY1) \text{ mg}$ ;

- Dose Compliance =  $(\text{Total Actual Doses} / \text{Expected Doses}) * 100\%$

The continuous endpoints of actual Dosing Days, exposure Time, total actual doses and dose Compliance will be summarized as described in Section 5.2.2 by treatment group based on SAS as defined in Section 4.

Number and percent will be reported for subjects in Actual Dosing Days categories ( $\leq 7$  days, 8 ~ 13 days, 14 days), and Dose Compliance categories ( $< 70\%$ ,  $70\% \sim 130\%$ ,  $> 130\%$ ).

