had a higher frequency of mortality (death), compared to patients treated with tofacitinib 5 mg twice a day or a tumor necrosis factor inhibitor medication (adalimumab or etanercept). In patients treated with tofacitinib 10 mg twice a day in other tofacitinib studies, the frequency of death has not been higher than the frequency of death in patients treated with tofacitinib 5 mg twice a day.

Minimizing risks: Patients will be evaluated at least once daily, depending on the level of care required of their overall condition after treatment initiation.

Toxicity monitoring: Patients will be monitored at least once daily after initiation of therapy, depending on the level of care required of their overall condition. On each day an H&P will be performed and the patient will undergo laboratory monitoring including hsCRP, ferritin, LDH, D-dimer, CBC, and CMP (SOC). If there is suspected toxicity from the therapy, the dose of tofacitinib may be reduced to 5 mg BID or stopped entirely, depending on the toxicity observed or suspected.

Research blood samples: The results of the research testing will not appear in the subject's medical file. No individual identifiers will be used for any testing. All samples and data are given a unique code to remove any identifying information. Any information that identifies the subject will be kept separate from the samples and this identified information will be kept until the study is complete.

With respect to prophylactic management of VTE, we will follow the institutional standard of care algorithm at the time of the study (**Appendix 1**).

Risk Mitigation Strategies

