- When a concomitantly used drug is a strong CYP3A4 inhibitor, OR when a co-administered drug is both a moderate CYP3A4 inhibitor and a strong CYP2C19 inhibitor (eg, fluconazole), a 50% reduction in dose is recommended. Therefore, a 5 mg BID dose should be used to achieve a similar exposure as that of 10 mg BID in a patient not receiving co-administered metabolic inhibitor.
 - Antivirals such as lopinavir and ritonavir are examples of potent CYP3A4 inhibitors. Cobicistat, which is used to increase concentrations of antiviral drugs, is also a potent CYP3A4 inhibitor. Examples of other co-administered drugs requiring dose reduction are ketoconazole, itraconazole, clarithromycin, telithromycin, and fluconazole (**Appendix 2**).
 - Tofacitinib dose reduction is not needed when co-administered with the following medication: azithromycin, hydroxychloroquine, chloroquine, remdesivir, favipiravir, oseltamivir, and ribavirin.
- A 50% dose reduction is recommended in patients who are in moderate or severe renal impairment (including patients on hemodialysis) and those in moderate hepatic impairment. Therefore 5 mg BID should be used in these patients, which will be

changed to 5 mg PO QD upon return to their clinical baseline (as defined by supplementary oxygen requirement).

- Tofacitinib should not be used in patients with severe hepatic impairment (Participants with Child-Pugh class C are excluded).
- Tofacitinib use is not recommended in patients receiving a potent CYP3A4 inducer (eg, rifampin, St. John's wort) or if they had discontinued use of a potent CYP3A4 inducer less than 28 days or 5 half-lives prior to the first dose of tofacitinib.

Required Tofacitinib Discontinuations:

In rare instances, it may be necessary for a participant to permanently discontinue study intervention (definitive discontinuation). Reasons for definitive discontinuation of study intervention include the following.

- WBC count <1000 /mm3
- Lymphocyte counts <250 cells/mm3.
- Absolute neutrophil counts <500 cells/mm3.
- Hemoglobin less than 8 g/dL.
- ALT or AST ≥5 times the ULN.
- Anaphylaxis or other serious allergic reaction.
- Diagnosis of venous thromboembolism.
- Any serious infection, including secondary bacterial pneumonia, or other safety event for which the investigator determines that continued treatment with tofacitinib is not in the participant's best interest.

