 - Antivirals such as lopinavir and ritonavir are examples of potent CYP3A4 inhibitors. Cobicistat, which is used to increase concentrations of antiviral drugs, is also a potent CYP3A4 inhibitor. Examples of other co-administered drugs requiring dose reduction are ketoconazole, itraconazole, clarithromycin, telithromycin, and fluconazole (**Appendix 2**).
 - Tofacitinib dose reduction is not needed when co-administered with the following medication: azithromycin, hydroxychloroquine, chloroquine, remdesivir, favipiravir, oseltamivir, and ribavirin.
- A 50% dose reduction is recommended in patients who are in moderate or severe renal impairment (including patients on hemodialysis) and those in moderate hepatic impairment. Therefore 5 mg BID should be used in these patients which will be changed to 5 mg PO QD upon return to their clinical baseline (as defined by supplementary oxygen requirement).
- Tofacitinib should not be used in patients with severe hepatic impairment (Participants with Child-Pugh class C are excluded).
- Tofacitinib use is not recommended in patients receiving a potent CYP3A4 inducer (eg, rifampin, St. John's wort) or if they had discontinued use of a potent CYP3A4 inducer less than 28 days or 5 half-lives prior to the first dose of tofacitinib.

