### 2.3. Study Design

The study concluded prematurely with a smaller-than-anticipated participant cohort, attributed to the return to pre-pandemic conditions as COVID-related restrictions eased during the recruitment phase. The situation warranted early termination of the study.

The study is a randomized, double blinded, placebo-controlled Phase 2b study of the efficacy and safety of tofacitinib in hospitalized adult (18-65 years old) male and female

patients with SARS-CoV-2 and pneumonia who require supplemental oxygen and have serologic markers of inflammation but do not need mechanical ventilation (see Inclusion criteria). Sixty patients will be recruited to receive tofacitinib or placebo in addition to standard of care (SOC) in a 2:1 ratio. Subjects will be screened during hospitalization. Patients with confirmed SARS-CoV-2 infection, and meeting all other Inclusion and Exclusion criteria, will be randomized to either treatment with tofacitinib or placebo in addition to SOC during hospitalization (dose adjusted, if required), with the exception of any immunomodulatory agents (as documented in the inclusion/exclusion criteria). Tofacitinib will be administered in a dose of 10 mg PO BID until return to their clinical baseline (as defined by need for supplementary oxygen) and will continue to be administered at 5 mg PO BID for a total duration of therapy of 14 days; follow-up off tofacitinib will continue up to Day 90. Because patients are likely to be discharged from the hospital soon after returning to clinical baseline, patients will continue to be administered tofacitinib 5 mg BID for a total duration of treatment of 14 days in order to prevent rebound of CRS that could theoretically occur with abrupt cessation of immunomodulatory therapy. In these cases, patients will be discharged home with a pill bottle labeled as investigational drug containing the appropriate number of pills (either tofacitinib or placebo). Rescue therapy is defined as IL-6 targeting agent or other non-FDA approved, compassionate use or expanded access when considered as medically necessary (AS REVIEWED BY THE PI) (Protocol section 6.1.2). Per protocol, subjects will discontinue from study treatment prior to taking rescue therapy.

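### SAP 6.4.3 scores dose compliance against the full regimen for everyone, so full adherence to the renal/hepatic regimen from Day 1 scores 50%

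*SAP*

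**What the plan says.** SAP 6.4.3 opens with a definition in words: "Dose Compliance is defined as the number of doses of study drug the subject took out of the expected total number of doses". The operative formula follows under "Expected Doses (by mg") and has two cases. If ADY1 (days from first dose to return to clinical baseline, inclusive) is 14 or more, the expected amount is 280 mg. Otherwise it is 140 + 10 × ADY1 mg. Compliance is total actual over expected, summarized as a continuous variable and in three categories: <70%, 70% to 130%, >130%.

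The two cases differ only in ADY1. Both assume 20 mg/day up to baseline and 10 mg/day afterwards. Yet SAP 2.3 describes study treatment as given "in addition to SOC during hospitalization (dose adjusted, if required"), and the protocol has three routes to a lower dose:

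- **Renal or hepatic impairment** (6.1.2, repeated in 6.1.11): "A 50% dose reduction is recommended in patients who are in moderate or severe renal impairment", and likewise in moderate hepatic impairment. The dose is 5 mg BID, "changed to 5 mg PO QD upon return to their clinical baseline".
- **CYP inhibitors** (6.1.2, 6.1.11): "a 5 mg BID dose should be used to achieve a similar exposure as that of 10 mg BID". No dose after return to baseline is stated for this route.
- **Suspected toxicity** (3.2.1): "the dose of tofacitinib may be reduced to 5 mg BID or stopped entirely".

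**The concern.** The denominator already follows each participant's own step-down day, so it is meant to track the regimen prescribed. It does so only for the full regimen. For a participant whose dose was halved under the protocol, the percentage and its category cannot be told apart from those of someone on the full regimen who missed half the tablets.

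The case is reachable. On hepatic and renal function, protocol 5.3.2 excludes Child-Pugh class C and eGFR below 40 (ALT/AST above 5 times the upper limit is a separate criterion). Moderate hepatic impairment therefore remains eligible, as may some renal impairment. Section 6.1.2 also applies the adjustments to changes in renal or hepatic function and to drug interactions that arise during treatment.

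At stake is the reading of one descriptive table. With few participants, one such person visibly moves it.

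**Working it through.** **Inputs.** Full regimen: 10 mg BID to clinical baseline, then 5 mg BID, 14 days in total (protocol 6.1.2). Renal/hepatic regimen: 5 mg BID, then 5 mg QD (6.1.2, 6.1.11). Formula and categories: SAP 6.4.3. As in that formula, day ADY1 counts at the pre-baseline dose. Total actual doses are taken in mg, with each placebo tablet counted as a nominal 5 mg.

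**The SAP's own figures.** 14 × 20 = 280 mg. For ADY1 < 14, 20 × ADY1 + 10 × (14 − ADY1) = 140 + 10 × ADY1 mg. Both reproduce; the arithmetic itself is sound. Write E for this expected amount.

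**Renal/hepatic regimen from Day 1, every tablet taken.** Actual = 10 × ADY1 + 5 × (14 − ADY1) = 70 + 5 × ADY1 mg. The score is (70 + 5 × ADY1) / (140 + 10 × ADY1) = 50%, because both phases are halved. In 5 mg tablets at ADY1 = 14 the ratio is the same: 28/56.

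**CYP inhibitor from Day 1, assuming 5 mg BID throughout.** Actual = 140 mg, so the score is 140/E.

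| ADY1 | E (mg) | Renal/hepatic taken (mg) | Score | CYP score, no further step-down |
|---|---|---|---|---|
| 1 | 150 | 75 | 50.0% | 93.3% |
| 6 | 200 | 100 | 50.0% | 70.0% |
| 7 | 210 | 105 | 50.0% | 66.7% |
| 10 | 240 | 120 | 50.0% | 58.3% |
| 14 or more | 280 | 140 | 50.0% | 50.0% |

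On this assumption the CYP score is below 70% only for ADY1 ≥ 7. If the halving is instead assumed to continue after baseline, it is 50.0% at every ADY1. The documents do not settle which applies.

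**Renal/hepatic regimen starting on Days 2–14.** With the full regimen before the start day and half of it from then on, the lowest score is 150/280 = 53.6% (ADY1 = 14, start Day 2). The highest is 265/270 = 98.1% (ADY1 = 13, start Day 14).

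**Toxicity reduction to 5 mg BID from Day d ≥ 2, assumed held to Day 14.**

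- If d ≤ ADY1, actual = 20 × (d − 1) + 10 × (15 − d) = 130 + 10 × d mg, and the score is (130 + 10 × d)/E. The range is 150/280 = 53.6% to 270/280 = 96.4%.
- At ADY1 = 7, d = 2 gives 150/210 = 71.4%, so no score is below 70% for ADY1 ≤ 7.
- At ADY1 = 8, d = 2 gives 150/220 = 68.2%, but d = 3 gives 160/220 = 72.7%.
- At ADY1 = 14, d = 6 gives 190/280 = 67.9% and d = 7 gives 200/280 = 71.4%.
- If d > ADY1, the full regimen is already 5 mg BID, so the score is 100%. The same holds for a CYP inhibitor started after baseline if no further step-down applies.

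**Effect of one participant** on the renal/hepatic regimen from Day 1. SAP 7 gives 24 randomized; assume all were dosed. Protocol 5.1 gives 1:1 allocation and SAP 2.3 gives 2:1, so both are shown.

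| Arm size | Shift in <70% category | Shift in mean compliance |
|---|---|---|
| 12 (1:1) | 1/12 = 8.3 points | 50/12 = 4.2 points |
| 16 (2:1) | 1/16 = 6.3 points | 50/16 = 3.1 points |
| 8 (2:1) | 1/8 = 12.5 points | 50/8 = 6.3 points |

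**The case against.** Several counter-arguments carry weight.

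- **The records already make the distinction.** Protocol 6.1.8 requires the reason for suspected compliance below 70% or above 120% to be entered in the CRF dosing log, and does not count a reason set by the protocol as a dosing error. This stands: the trial's records are designed to separate a directed reduction from non-adherence. It does not repair the SAP table, which loses that distinction.
- **The measure may be percent of the planned full course.** Its denominator runs to Day 14 even for participants who die or must stop under 6.1.2 and 6.3.7. This is a fair reading of what the formula does, and it shows that discontinuation needs a rule too. But the SAP calls the measure compliance against expected doses and tailors it to ADY1, while total actual doses, dosing days and exposure time are summarized separately.
- **Doses could mean administrations.** The definition in words speaks of a number of doses, and total actual doses has no stated unit. Counting administrations, the Day 1 renal/hepatic case scores (14 + ADY1)/28, from 53.6% at ADY1 = 1 to 100% at 14. The 50% therefore rests on the mg formula, which is the one the SAP writes out.
- **It may affect nobody.** True. The protocol discourages strong CYP3A inhibitors, moderate renal impairment is not defined, and no count of reduced-dose participants is given.

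A reader might infer that every dose reduction is scored as non-compliance. The documents do not support that: CYP and toxicity reductions can score 70% or more, and 100% when they start after baseline with no further step-down.

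**Conclusion.** The formula gives a misleading score for a regimen that the protocol itself directs. Full adherence to the renal/hepatic regimen from Day 1 scores 50% at every ADY1 and is always classed <70%; a start on Days 2–14 scores 53.6% to 98.1%. For CYP-inhibitor or toxicity reductions to 5 mg BID, a score below 100% requires a start on or before the day of return to baseline if no further step-down applies. A score below 70% requires ADY1 ≥ 7 (CYP from Day 1, no further step-down) or ADY1 ≥ 8 with an early start (toxicity from Day 2 or later).

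These figures assume actual doses in mg and, for the last two routes, the dosing patterns stated in the check. The gap is in the definition, not in the SAP's arithmetic.

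It would be tempting to conclude that efficacy results are affected or that participants were in fact misclassified. Neither follows. Compliance defines no analysis set and feeds no endpoint, SAP version 2.0 is descriptive only, and the number of participants affected may be zero. Low severity.

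**What to change.** In SAP 6.4.3, define the expected amount as the sum over Days 1–14 of the daily amount prescribed for that participant under the protocol's dose-modification rules. Use mg or 5 mg tablets, treat placebo the same way, and state the same unit for total actual doses. For the renal/hepatic regimen from Day 1 the denominator becomes 70 + 5 × ADY1 mg, and full adherence scores 100%. State also whether days after death or protocol-mandated discontinuation count in the denominator.

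This needs the prescribed regimen by day. The pharmacist records the number of tablets each patient will receive (protocol 6.1.6) and administration details go on the CRF (6.1.2). The documents do not say whether the count is updated at step-down or at a mid-course reduction, so this must be checked.

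If it was not recorded, keep the present formula for full-regimen participants and list reduced-regimen participants on a separate footnoted line. Identify them from the dosing log (6.1.8) together with the administration records, because log entries are required only when compliance outside 70% to 120% is suspected.

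The cost is one formula and one reprogrammed table, without a protocol amendment. No dose or clinical rule is proposed.
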